10.3 Missing values

According to chapter 6.5 failures to the common practice intervals of patient visits will not constitute a breach or violation of the protocol. All missing values are documented as missing and not replaced. Instructions for the minimum documentation for each patient will be established in the statistical analysis plan.

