6.2 Number of Patients to be Enrolled

The PMOS will include up to 2000 patients with active moderate to severe Crohn's disease.

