6.4 Study Duration

The observation period for each individual patient starts with the administration of the initial dose of Adalimumab and ends after 60 months.

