Crohn's related surgery (incl. bowel surgery & number of surgeries)

Concomitant diseases

Concomitant medication (Crohn's related)

Crohn's disease activity before treatment

CDAI

Current manifestation of Crohn's disease and extraintestinal manifestation (EIM)

Laboratory values (leukocyte and thrombocytes count, hematocrit, C-reactive protein, gamma-glutamyl transpeptidase)

Pre-medication (Crohn's related): 5-ASA/Suflasalazine, steroids, immunosuppressants, TNF-inhibitors (incl. duration of treatment, reason for discontinuation; for prior adalimumab treatment: additionally documentation of former maintenance dose and interval), other biologicals

Average number of moderately severe to severe bouts of active disease per year over the past 3 years

Examinations prior to initiation of adalimumab therapy

Tuberculosis diagnostics & result (only if adalimumab therapy recently started)

Imaging techniques for disease activity assessment (i.e. endoscopy, ultrasonography, MRI or CT scan)

Mucosal healing status

Status for chronic hepatitis B

Initiation of adalimumab therapy

Date of initiation

Dose & interval

Follow-up Data (months 3, 6, 9, 12, 18, 24, 30, 36, 42, 48, 54, 60)

Weight

Adalimumab treatment continued/abrogated (reason for abrogation)

Adverse events/SAE

Crohn's disease activity during treatment

CDAI

Current manifestation of Crohn's disease, Fistula and EIM (incl. comparison of current disease activity with previous visit)

Crohn's related surgery since last visit (incl. bowel surgery & number of surgeries)

Mucosal healing

Change of adalimumab treatment (incl. change in dose & interval; if discontinued: reason for discontinuation; restart)

Change of concomitant Crohn's-related medication (steroids, immunosuppressants, antibiotics)

Laboratory values (leukocyte and thrombocytes count, hematocrit, C-reactive protein, gamma-glutamyl transpeptidase)

Imaging techniques for disease activity assessment since last visit (i.e. endoscopy, ultrasonography, MRI or CT scan)

Patients Questionnaire (months 0, 3, 6, 12, 24, 30, 36, 42, 48, 54, 60)

S-IBDQ (standard questionnaire)

Crohn's related hosptalization (within previous 3 months; incl. number of hopitalizations, duration of hospitalization)

Crohn's related work productivity impairment (within previous 3 months)

Final Data (month 60)

Global assessement of efficacy and safety, change of current Crohn's related medication, and adverse events

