10.1 Sample size calculation

For this postmarketing observational study no sample size calculation was performed. The sample size of 2000 should lead to a sufficient number of patients with data at month 60 to perform adequate long-term safety and effectiveness analysis, assuming an annual drop-out rate of 20% to 30%.

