10.2 Study population

The study population contains data of all documented patients. According to chapter 5 the objective of the study is the Adalimumab therapy in patients with Crohn's disease under routine conditions. Therefore a separate analysis for intention to treat population and per protocol population is not planned.

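### Missing values stay unreplaced while 67–83% of patients may have no month-60 data, and the protocol plans nothing to examine that loss

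*Protocol*

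**What the plan says.** - Protocol 10.3 (Missing values): "All missing values are documented as missing and not replaced". The only item this section hands to the SAP is the minimum documentation required per patient.
- Protocol 10.1 (Sample size calculation): "For this postmarketing observational study no sample size calculation was performed". It continues: "The sample size of 2000 should lead to a sufficient number of patients with data at month 60", and this is said "assuming an annual drop-out rate of 20% to 30" per cent.
- Protocol 10.2 (Study population) defines one population, everyone documented, and adds: "Therefore a separate analysis for intention to treat population and per protocol population is not planned".
- Protocol 6.2 and 6.4 set up to 2000 patients and 60 months of observation each.
- Protocol 10.4 and 10.5 list the proportion achieving remission, time to remission, logistic and Cox regression, centre effects, subgroups and descriptive statistics. They name neither a denominator for remission at a given visit nor any analysis of drop-out.
- Protocol 6.5 lists the S-IBDQ through month 60. It places the global assessment of efficacy and safety under a block labelled for month 60. CDAI and the other items are documented only where routine care assesses them. Follow-up forms record whether adalimumab was stopped, why, and whether it was restarted.

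**The concern.** The primary objective (Protocol 5) is long-term efficacy and safety, and 10.1 rests the long-term analysis on patients who have month-60 data. On the protocol's own drop-out figures those patients are a minority. If missing values are left missing and remission is calculated among those observed, each later visit describes a smaller and possibly more selected group. In a single-arm cohort no comparator shares the attrition.

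Patients doing badly may well be the ones who leave. The late remission rate and mean S-IBDQ could then rise without any patient improving. The interval around the rate would reflect only sampling error in the remainder and would look reassuringly narrow.

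The global assessment raises a separate issue. If the final form is completed only as scheduled at month 60, early leavers have none, and no later analysis can recover it.

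**Working it through.** **Inputs from the protocol.** N = 2000, an upper limit (6.2, 10.1). Annual drop-out d = 0.20 to 0.30 (10.1). Follow-up is 5 years (6.4).

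**Inputs not in the protocol, assumed.** p is remission among patients observed at month 60, taken as 40% to 70%. q is remission among patients with no month-60 value, varied from none to all.

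**The plan's own figure.** The 2000 cannot be reproduced, because 10.1 says no calculation was done and gives no target number for month 60.

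**Step 1: patients remaining.** N × (1 − d)^k after k years, with d constant and applied to those still present. Taking d as a share of the starting 2000 would leave nobody after five years even at 20% (1 − 5 × 0.20 = 0), so compounding is the only workable reading.

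| Month | d = 20% | d = 30% |
|---|---|---|
| 12 | 1600 | 1400 |
| 24 | 1280 | 980 |
| 36 | 1024 | 686 |
| 48 | 819 | 480 |
| 60 | 655 | 336 |

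The retained share f at month 60 is 0.8^5 = 32.8% or 0.7^5 = 16.8%. So 67.2% or 83.2% have no month-60 value. These counts assume full enrolment and that every retained patient is assessed, so actual numbers may be lower.

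**Step 2: nominal precision and whole-cohort remission.** Half-width = 1.96 × √(p(1 − p)/n). Whole-cohort remission = f·p + (1 − f)·q.

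| d | p observed | 95% half-width (points) | q = 0 | q = p/2 | q = p | q = 1 |
|---|---|---|---|---|---|---|
| 20% | 40% | 3.8 | 13.1% | 26.6% | 40% | 80.3% |
| 20% | 50% | 3.8 | 16.4% | 33.2% | 50% | 83.6% |
| 20% | 70% | 3.5 | 22.9% | 46.5% | 70% | 90.2% |
| 30% | 40% | 5.2 | 6.7% | 23.4% | 40% | 89.9% |
| 30% | 50% | 5.4 | 8.4% | 29.2% | 50% | 91.6% |
| 30% | 70% | 4.9 | 11.8% | 40.9% | 70% | 95.0% |

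**Step 3: reading the table.** The q = 0 and q = 1 columns are limits, not predictions. If leavers remit at half the observed rate, the observed-case figure is too high by p(1 − f)/2. At 20% drop-out that is 13.4 to 23.5 points; at 30% it is 16.6 to 29.1 points. This is roughly three to seven times the nominal half-width. If q = p there is no bias, and if q exceeds p the bias reverses.

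**The case against.** **A reader might infer that 10.3 fixes a completers-only analysis.** It does not. It bars replacement and sets no denominator. Reporting remission over all documented patients, with missing as its own category, would comply with 10.2 and 10.3. So would a mixed model on available visits, which needs no imputation. Completer means appear nowhere in the text.

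**A reader might infer that late results are bound to look too favourable.** That requires leavers to do worse than those who stay. It is likely in a single-arm treatment cohort, but the protocol gives no data on it. A form field for the reason for stopping does not show what the reasons will be.

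**A reader might equate drop-out with stopping adalimumab.** Section 10.1 does not define drop-out. Section 6.4 ends observation at 60 months rather than at discontinuation, and 6.5 records restarts. Some patients who stop may still give data.

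**The named remission analyses are less exposed.** Achieving remission and time to remission use early follow-up, and the Cox models censor, although informative censoring remains possible. At month 12, 1400 to 1600 patients remain.

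**The SAP could supply the missing analyses.** Section 10 refers detailed procedures to it, and it is not at hand. Denominators and sensitivity analyses often belong there.

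**The final form may not be limited to month 60.** Section 9 mentions a final report without that limit, so the claim that early leavers can never have one is a reading of 6.5, not a stated rule.

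All these limits stand, and they narrow the point. They do not remove it. The no-replacement rule is protocol text, so an SAP that imputed would need to be reconciled with it. The expected loss is the protocol's own figure, and 10.1 leans on month-60 data regardless. A form not completed when a patient leaves cannot be repaired by an SAP.

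**Conclusion.** The point holds for late by-visit results. With 2000 enrolled and constant drop-out of 20% to 30% a year, about 655 to 336 patients (33% to 17%) would have month-60 data. The protocol pairs this with a no-replacement rule and no stated examination of the loss. Observed-case remission, S-IBDQ and global assessment at late visits would describe a selected remainder and are likely, but not certain, to flatter the treatment.

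For assumed observed remission of 40–70%, uncertainty from the missing patients far exceeds the nominal half-width of about 4–5 points. The conservative bound is 13–23% of all starters at 20% drop-out and 7–12% at 30%. These remission figures are illustrative, since the protocol gives no remission rate. The retention figures depend only on its own numbers and on compounding.

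The bound should not become the main estimate. With leavers counted as failures, month-60 remission cannot exceed 32.8% or 16.8% even if every retained patient is in remission, so it would largely measure retention. For a non-interventional, single-arm study with less exposed early results, this is a point that should be fixed, not one that invalidates the plan.

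**What to change.** Keep the raw data unreplaced and make three changes.

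1. In 10.3 and 10.4, show every by-visit remission rate with its denominator and the numbers and reasons for loss. Beside the observed-case rate give (i) an all-starters rate counting lost or stopped patients as not in remission, labelled a conservative bound and not the main estimate, and (ii) a multiple-imputation sensitivity analysis. Word 10.3 so that its no-replacement rule applies to the recorded data and does not exclude (ii).
2. In 10.4, analyse change in CDAI and S-IBDQ with a mixed model using all available visits.
3. In 6.5, have the final form completed at month 60 or at premature end of observation, whichever comes first.

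The cost is some extra analysis, a few sentences of protocol text and one line on a form. A less favourable figure will appear beside the observed-case rate. The mixed model and the imputation both rest on assumptions about why data are missing, so neither settles the question alone. The third change matters most early, because assessments not collected when patients leave cannot be obtained later.

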10.4 Biometric concept

The aims of the biometric concept for the statistical analysis include:

- Assessment of the safety of the Adalimumab therapy by evaluation and registration of side effects
- Assessment of the efficacy of the Adalimumab therapy by evaluating the proportion of patients achieving remission (remission as defined according to CDAI or HBI scores)
- Assessment of factors of influence to remission (logistic regression models), e.g. duration of therapy, concomitant medication in the medical history, extraintestinal manifestation, kind of Crohn's disease (fistula, stenoses)
- Assessment of the duration until remission
- Assessment of factors influencing time until remission (Cox regression models)
- Assessment of centre effects
- Subgroup analyses based on the results of the regressions analyses

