10.5 Statistical analyses

The study population will be described including all documented variables (absolute and relative frequency, mean, median, quantiles, range etc.). The incidence of side effects of

the Adalimumab therapy will be described according to the physician's statement. The level of statistical significance is established to 5%, a multiple fit to a global level of significance is not planned.

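### Treatment duration, known only after follow-up, is named as a factor in the logistic model for remission and can look like a predictor when it has no effect

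*Protocol*

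**What the plan says.** Protocol section 10.4 lists the aims of the analysis. One is "Assessment of factors of influence to remission (logistic regression models), e.g. duration of therapy". The same list goes on with "concomitant medication in the medical history, extraintestinal manifestation, kind of Crohn's disease (fistula, stenoses"). Separate items cover the time until remission, Cox models for factors influencing it, and "Subgroup analyses based on the results of the regressions analyses".

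Section 10.5 sets the testing rule: "The level of statistical significance is established to 5%, a multiple fit to a global level of significance is not planned". Section 10.1 states "For this postmarketing observational study no sample size calculation was performed" and justifies 2000 patients by "assuming an annual drop-out rate of 20% to 30" per cent.

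Section 6.5 has each follow-up form record whether adalimumab was continued or stopped, the reason, and any restart. Section 10.2 puts all documented patients into one analysis population. Section 10 leaves procedural detail to a statistical analysis plan, which is not at hand.

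**The concern.** A factor said to influence an outcome should be known before the outcome can occur. Time on adalimumab is not: its value is settled during follow-up, alongside remission. Two mechanisms can then link it to remission without any effect of duration.

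- **Unequal opportunity.** If remission means being in remission at any visit on treatment, a patient followed for 60 months has 12 chances to be counted and a patient who leaves after month 3 has one.
- **Reverse causation.** If patients not in remission stop sooner, remission status produces the duration.

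An ordinary logistic model has no time axis and cannot separate either mechanism from a real benefit of longer treatment. Remission belongs to the primary objective in section 5, so a duration coefficient of this kind could be read as evidence that staying on the drug brings remission. A covariate selected this way could also feed the subgroup analyses, which section 10.4 derives from the same regressions.

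**Working it through.** The protocol states no remission rate, effect size or stopping ratio, so there is no figure of its own to reproduce. The check asks what the named model returns when duration truly has no effect.

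**Inputs from the protocol.** Visits at months 3, 6, 9, 12, 18, 24, 30, 36, 42, 48, 54 and 60 (section 6.5); 2000 patients and 20–30% annual drop-out (section 10.1); 5% tests without adjustment (section 10.5).

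**Assumptions.** Mean per-visit remission 0.42; a patient-level random intercept on the logit scale with SD 1; drop-out treated as the end of both therapy and observation; two-sided tests.

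**Hand check of unequal opportunity.** With a constant remission probability of 0.42 and independent visits, the chance of at least one remission in k visits is 1 − 0.58^k:
- k = 1: 0.42
- k = 4: 1 − 0.113 = 0.89
- k = 12: 1 − 0.001 = 0.999

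Variation between patients softens this but does not remove it.

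**Simulation, no effect of duration** (200,000 patients, logistic regression on years of therapy):

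| Outcome | Stopping hazard, non-remitters to remitters | Spurious OR per year |
|---|---|---|
| Ever in remission | 1 (random) | about 1.9 (20% a year) to 2.1 (30% a year) |
| Remission at last visit | 1 (random) | 1.00 |
| Remission at last visit | 1.5 | about 1.1 |
| Remission at last visit | 2 | about 1.2 |
| Remission at last visit | 3 | about 1.3 |

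In the first row, about 66% of patients with 3–12 months of therapy are ever in remission, against 96% of those with 60 months. With larger between-patient variation (SD 2 or 3, 20% a year) the first-row OR falls to 1.38 and 1.22.

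**How often it would reach significance.** A simpler model was used: 40% in remission with status fixed per patient, about 25% a year stopping, and three null baseline factors also in the regression (500 runs each).

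| Stopping ratio | Median OR per year | P(p < 0.05), n = 500 | P(p < 0.05), n = 2000 |
|---|---|---|---|
| 1 | 1.00 | 4.6% | 5.6% |
| 1.25 | 1.11 | 56% | 98% |
| 1.5 | 1.20 | 93% | 100% |
| 2 | 1.37 | 100% | 100% |

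With remission counted as ever reached while treated (assumed constant hazard 0.25 a year) and stopping independent of it, the OR is about 1.85 and the rejection rate 100% at both sizes. For orientation, 2000 × (1 − d)^5 leaves 655, 475 and 336 patients at month 60 for d = 20%, 25% and 30%.

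**The other named factors.** These are mainly history or disease type, and when null each carries the ordinary 5%. For four null factors, assuming independence, the chance of at least one false positive is 1 − 0.95^4 = 18.5%. For the three other than duration it is 1 − 0.95^3 = 14.3%.

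**The case against.** **The term is not defined.** Section 6.5 also collects, at baseline, how long earlier TNF inhibitors were given, with extra detail for prior adalimumab, and section 6.5.1 provides follow-up for centres from an earlier adalimumab study. If earlier therapy was meant, the covariate is legitimate. This stands as an ambiguity. Neighbouring items in section 10.4 speak of adalimumab therapy, so on-study exposure is the natural reading, and the line needs rewording either way.

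**The analysis plan may settle it.** The factors are examples, and the outcome visit, coding and any landmark are ordinary content for that plan. Their absence from the protocol is therefore no finding. The covariate itself, however, is stated in the protocol, and the plan would have to depart from section 10.4 to remove it.

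**Drop-out is not the same as stopping treatment.** Section 6.4 has observation run to 60 months, and restarts are recorded, so a patient off drug may still be seen. This stands: unequal opportunity operates only if observation, or the counting of remission, ends with treatment. Reverse causation does not depend on that.

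**The bias is conditional.** This also stands. For last-visit remission with stopping unrelated to remission, the OR is 1.00 and the test holds its nominal level.

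**Multiplicity.** A reader might infer that a crop of false predictors and subgroups is bound to be reported, because "a multiple fit to a global level of significance is not planned". The protocol does not support that. It names four factors and does not fix a long list; 20 null factors would give 1 − 0.95^20 = 64%, but that number of tests appears nowhere in it. Unadjusted testing is openly disclosed and conventional in a single-arm observational study, and the subgroup analyses may be purely descriptive.

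**Conclusion.** The point holds for one covariate. On the natural reading, section 10.4 places a post-baseline variable in a logistic model for remission, where it can appear to be a predictor with no effect behind it. The size depends on assumptions the protocol does not supply. It is large for an ever-in-remission outcome if observation ends with treatment, and modest for last-visit remission if non-remitters stop sooner. It is absent for last-visit remission if stopping is unrelated to remission. Under either of the first two conditions a significant duration term is very likely at 2000 patients, even with a stopping ratio of 1.25.

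It would go too far to say that spurious predictors in general will be reported, or that response is shown to drive stopping. The protocol says neither, and a real relation between longer treatment and remission could coexist with the artefact. The remission proportion does not depend on this covariate. The correction should be made, but the defect does not undermine the study's main results.

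**What to change.** In section 10.4:

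1. Delete time on adalimumab as a fixed covariate. If disease duration or the duration of earlier therapy was meant, say so.
2. Restrict the logistic and Cox factor models to variables known at first dose, such as disease duration, prior TNF-inhibitor use, baseline concomitant medication, fistula, stenosis and extraintestinal manifestations. In the logistic model, take remission at a fixed visit.
3. If on-study exposure is of interest, examine it only by a landmark analysis or as a time-dependent covariate.

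Secondary: name the main baseline subgroups in the statistical analysis plan before the database is opened. Report any subgroup chosen from the regressions as exploratory, with confidence intervals.

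The cost is a few lines of text and some extra analysis work. On-study duration is no longer reported as a simple predictor. Data collection does not change.

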with the terms of the marketing authorization. Data on the safety and efficacy of Adalimumab will be collected from initial dosing and up to 60 months of therapy.

Well-designed observational cohort studies including a very strict study protocol and monitoring, are indispensable to complement the knowledge gained from randomized controlled trials with important real-life data. The gain in experience was recently demonstrated in the German register RABBIT in rheumatoid arthritis patients. RABBITT provided information that the majority of patients with various comorbidities, concomitant medications, dosing schemes, and disease states, who would not fulfill the inclusion criteria of a major trial, benefit from biologic therapy (14).

5. Study Objective

The primary objective of the non-investigational study (PMOS) is to demonstrate long-term efficacy and safety of Adalimumab in patients with Crohn's disease under routine conditions and to evaluate the proportion of patients achieving remission and the time to remission induction.

Secondary objectives include: Improvement/resolution of signs and symptoms of the acute Crohn's disease (CDAI –100), rate of adverse events, and long-term improvement of patients QOL.

Further, the observation study protocol enables physicians to characterize patients that fulfill criteria for Adalimumab treatment thus ensuring the requirements of reimbursement.

6. Investigational Plan

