6.5 Study Conduct

This postmarketing observational study will be conducted in a single-arm, multi-center format.

6

Observational studies are intended to gather findings in the use of marketable medicinal products. Their special feature is that they do not influence, as far as this is possible, the physician in charge of the treatment in his diagnosis or choice and implementation of therapy for the individual case.

Adalimumab must not be prescribed for the purpose of including a patient in this observational study. Physicians are encouraged to treat their patients as in routine clinical practice. The patient is only identified for the study after the decision on the therapy had been made.

Patients who have active severe Crohn's disease and start treatment with Adalimumab in normal clinical settings according to label are documented. Adalimumab will be administered by sc injection. The dose regimen is recommended following the approved label: Either an initial dose of 160 mg adalimumab sc at Week 0 followed by 80 mg adalimumab sc at Week 2, or an initial dose of 80 mg adalimumab sc at Week 0 followed by 40 mg adalimumab sc at Week 2. Starting at Week 4 all subjects will receive 40 mg every other week (eow) sc in an open-label fashion. The PMOS documentation starts with the first application of Adalimumab, and is repeated at month 3, 6, 9, 12, 18, 24, 30, 36, 42, 48, 54, and 60.

The follow-up observation period is planned for five years and is focused on maintenance of efficacy and safety information during normal clinical settings. The physicians will follow up the patient via regular office visits at intervals as determined by routine clinical practice or as recommended by national guidelines. It is expected that follow up visits will be performed every three months during the first year and every six months during the subsequent four years. Baseline and follow up visits will be reported on different forms. Failure to observe these usual practice intervals of patient visits will not constitute a breach or violation of the protocol.

The following data will be documented (if assessed in routine care):

Baseline Demographic Data (month 0)

Age

Gender

Height

Weight

Smoking behavior

Informed Consent

Informed consent signed by patient

Medical History

History of Crohn's disease

- Date of first diagnosis
- First manifestation of Crohn's disease

Local of luminal disease

Fistula

Stenoses

Extra-intestinal manifestation

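### Section 10.4 names Cox regression for time to remission, but remission is seen only at documentation visits from month 3 on, so the model needs a grouped-time or interval-censored form.

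*Protocol*

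**What the plan says.** Protocol section 5 includes in the primary objective "to evaluate the proportion of patients achieving remission and the time to remission induction". Section 10.4 defines remission by CDAI or HBI score. Besides an assessment of the duration until remission, it lists "Assessment of factors influencing time until remission (Cox regression models)".

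Section 6.5 sets when a score can be recorded. After the first dose, documentation "is repeated at month 3, 6, 9, 12, 18, 24, 30, 36, 42, 48, 54, and 60". Visits are expected "every three months during the first year and every six months during the subsequent four years", but they are "regular office visits at intervals as determined by routine clinical practice", and "Failure to observe these usual practice intervals of patient visits will not constitute a breach or violation of the protocol". Items are documented only where routine care assessed them, and section 10.3 leaves missing values unreplaced.

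Section 10 refers detailed procedures to a statistical analysis plan, which is not at hand. The protocol does not mention interval censoring, ties or the date to be used for the event.

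**The concern.** A score-based remission is first known at the first assessed visit at which it is present. All that is then known is that it began after the last assessed visit without remission. In its usual form a Cox model takes one date as the event time. If that is the visit date, two things follow.

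- **The time itself.** Nothing is documented between the first dose and month 3. The protocol's own background (section 3) cites a 4-week trial showing induction of remission. Part of the effect may therefore fall inside the unobserved window, although its speed is a primary aim.
- **The factors.** Rounding event times up to visits produces heavy ties and weakens real effects. If one level of a factor has fewer visits or fewer recorded scores, its remissions are found later and it appears to remit more slowly.

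Section 10.4 also plans subgroup analyses based on the regression results, and section 10.5 sets an unadjusted 5% level. A spurious factor could therefore be carried forward.

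**Working it through.** The protocol gives no hazard ratio, event number or expected median, so there is no planned figure to reproduce. True medians, missed-score rates and visit differences below are assumptions. Remission times are taken as exponential, and remission once reached is taken to be still present at the next assessed visit.

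**Step 1: the median.** With true median m months, the share of remissions first seen at month 3 is 1 − 2^(−3/m).

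| Assumed true median (months) | 1 | 2 | 3 | 6 | 12 |
|---|---|---|---|---|---|
| Share first seen at month 3 | 88% | 65% | 50% | 29% | 16% |
| Median read from nominal visits (months) | 3 | 3 | 3 | 6 | 12 |

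The flat result at 3 does not depend on the exponential shape. Whenever at least half of the patients remit by month 3, the visit-date median is 3.

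**Step 2: visit timing unrelated to the factor.** Simulation with 1,000 patients, one binary factor, 25% annual dropout (the middle of the 20% to 30% in section 10.1), two-sided 5% and 40 runs per cell. Cox regression was fitted to the first visit in remission.

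- True hazard ratio 1.0, nominal visits or visits with a 0.5-month random shift: estimates 0.98 to 1.01, rejection at most 7%. There is no spurious effect.
- True hazard ratio 1.5, nominal visits:

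| Assumed median (months) | 2 | 6 | 12 |
|---|---|---|---|
| Efron ties | 1.42 | 1.46 | 1.48 |
| Breslow ties | 1.22 | 1.37 | 1.43 |

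On the log scale at a 2-month median, Efron keeps ln 1.42 / ln 1.5 = 0.351/0.405 = 86% of the effect. Breslow keeps ln 1.22 / ln 1.5 = 0.199/0.405 = 49%.

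**Step 3: visit timing or completeness related to the factor.** Same simulation, Efron ties, true hazard ratio 1.0. Rejection rates are in brackets.

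| Assumed difference between factor levels | Median 2 | Median 6 | Median 12 |
|---|---|---|---|
| Score missed at 10% vs 30% of visits | 1.30 (100%) | 1.12 (40%) | 1.05 (12%) |
| Three- vs six-monthly visits in year 1 | 1.92 (100%) | 1.20 (70%) | 1.06 (20%) |
| Visits 1 month early vs 1 month late | 1.08 (28%) | 1.01 (0%) | 1.00 (3%) |

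A milder case, 10% versus 20% missed scores, gave 1.14 at a 2-month median and 1.06 at 6 months.

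**Step 4: the alternative model.** A proportional-hazards model with an interval-censored likelihood and piecewise-constant baseline was run at medians 2 and 6. It covered nominal visits, 10% versus 30% missed scores, and three- versus six-monthly visits, with 60 runs each. A true 1.0 gave 0.98 to 1.01 and a true 1.5 gave 1.48 to 1.50.

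Rejection under the null was 7% to 13% per cell. Over the six null cells that is about 34 of 360, or 9.4%, which is above 5%. The standard error came from the optimiser's approximate curvature matrix. These runs therefore support the point estimates but do not show that the test holds its level.

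**The case against.** The strongest reply is that section 10.4 is a list of aims and that the statistical analysis plan may already handle interval censoring. The protocol never says that the visit date is the event time. Complementary log-log and interval-censored models are forms of the same proportional-hazards model with the same hazard ratio, so Cox regression is not wrong in itself. This stands, and the figures above hold only if the model is fitted to visit dates. It does not dispose of the point. The protocol fixes the model family for an event that its own schedule makes interval-censored, and no analysis plan can supply observations before month 3.

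A reader might infer that the estimated factors largely measure the visit schedule. The documents do not support that. Step 2 shows only attenuation, mild with Efron ties, when visit timing is unrelated to the factor. A reader might also infer that hazard ratios for centre type, severity or fistula are biased. No section ties visit frequency or score completeness to any of these, and section 6.5 expects three-monthly visits in year 1 for everyone. The value of 1.92 needs a complete schedule split between factor levels and a 2-month median.

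It is also fair that the primary objective names time to remission and not its predictors. The factor analysis, with no multiplicity adjustment, reads as exploratory. That limits the consequences for factors but leaves the problem with the time itself.

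**Conclusion.** The concern holds in limited form.

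- **Certain from the documents:** remission is interval-censored, and time to remission before month 3 cannot be resolved. A visit-date median reads 3 months for any true median up to 3 months on the nominal schedule.
- **Conditional on fitting Cox to visit dates:** real factor effects are attenuated. At an assumed 2-month median a hazard ratio of 1.5 becomes about 1.42 with Efron ties and 1.22 with Breslow ties.
- **Conditional also on an association the documents do not show:** a null factor can appear active. At medians of 2 to 6 months the ratio is about 1.30 to 1.12 for 10% versus 30% missed scores, and about 1.9 to 1.2 in the extreme case of three- versus six-monthly visits. It fades as remission becomes slower.

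The change should be made. It does not call the study into question.

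**What to change.** In section 10.4, specify the proportional-hazards model in grouped or interval-censored form, with the event lying between the last assessed visit not in remission and the first assessed visit in remission. A discrete-time complementary log-log model suits patients assessed at every nominal visit. Where visits or scores are missed, the interval-censored form is needed.

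Report cumulative remission by months 3, 6, 12 and 24 from an interval-censored estimate, in place of a median of visit dates. State that speed of induction within the first 3 months cannot be estimated. A table of visit frequency and score completeness by factor would show whether the association in step 3 exists.

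The cost is slightly more programming and the loss of a simple median. No visits are added and the study stays non-interventional. Two limits remain. The model cannot recover timing before month 3. It also assumes that visits are not triggered by the remission state itself. How to treat stopping adalimumab before remission is a separate estimand choice and is not part of this change.
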